2. SYNOPSIS

Study Title	A retrospective observational analysis of a cohort with Heart Failure with Preserved Ejection Fraction from a BNP pathway clinic
Problem statement	Heart failure with preserved ejection fraction (HFpEF) is a complex condition with various causes that is not yet fully understood. Most significantly there is no single method of diagnosing or treating the condition. Recently a novel non-invasive diagnostic criterion to predict the likelihood of HFpEF was proposed by Reddy et al. (2018) called H2FPEF. The main limitation of this study was the use of a single centre population from the Mayo clinic in Rochester, US. Another limitation is that the H2FPEF diagnostic criterion consists of common and often co-existing conditions which could as a result overestimate HFpEF probability. The aim of the investigators is to retrospectively test the H2FPEF criteria on the population at Queen Alexandra Hospital (QAH) in Portsmouth, which is of a lower socio-economic status and greater ethnic diversity. Implications of the project if H2FPEF is proved to be generalizable to the population is that it can be used within the Trust and rolled out to others. This would allow diagnosis to be made quicker and more cost effectively using echocardiography and without the need for invasive cardiac catheterisation. On the other hand if H2FPEF is found not to be applicable to the population then further research would be required to find the ideal diagnostic tool.
Research question / hypothesis	The investigator's hypothesis is that when H2FPEF criteria is compared against retrospectively held data for the patient population at QAH that this will overestimate the probability of HFpEF
Study Design	The study is a single-centre retrospective observational analysis
Study Participants	Patients who attended heart failure clinics at Queen Alexandra Hospital between January 1st 2016 – December 31st 2016
Planned Sample Size	2000
Follow-up duration	1 year
Planned Study Period	04/10/2019 – 30/04/2020
Primary Objective	The primary objective of the investigator's project is to test if the H2FPEF score accurately predicts HFpEF on the population at Queen Alexandra Hospital.

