Secondary Objectives	
 • Investigate if H2FPEF overestimates HFpEF diagnosis on the patient population when compared against known BNP levels. • To evaluate if H2FPEF can be validated on the patient population and be utilised to improve patient pathway for HFpEF. • To monitor patient responses to treatments and care for one year.
Primary Outcome Measure	To assess the predictive accuracy of H2FPEF at predicting HFpEF on the patient population as calculated by logistic regression, with diagnostic accuracy being assessed by sensitivity and specificity calculations.
Secondary Outcome Measures	
 • ANOVA will be performed to provide one simultaneous evaluation of the data to determine if there is a significant difference between

	H2FPEF score and diagnosis of HFpEF. •To assess number of hospital admissions and any changes in treatment/ care after one year for the population.
--	--

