In response Reddy et al (2018) recently proposed non-invasive diagnostic criteria called H2FPEF which assesses patients based on body mass index (BMI), the number of hypertensive medications they take, presence of AF, pulmonary pressure, age and filling pressure. The advantage of the H2FPEF score is that it uses only non-invasive echocardiography data alongside routine clinical data making it easy to derive. However one key limitation of their study is the population they used was all from the Mayo clinic and so the generalisability of their results has not been tested for other populations, such as those of lower socioeconomic status like in Portsmouth. A further limitation is the parameters chosen to create H2FPEF are all relatively common morbidities and usually co-exist, making it likely that it will over diagnose HFpEF.

Research questions:

The main research question the investigators are investigating is whether the H2FPEF criteria proposed by Reddy et al. (2018) is an accurate predictor of HFpEF on the patient population at QAH. In the original paper by Reddy et al. (2018) they created and tested H2FPEF criteria on their study population from the Mayo clinic, Rochester, US. This population is predominantly Caucasian and of a high socioeconomic status and so lacks generalisability. In response the investigators are testing the H2FPEF criteria on the population at QAH which is of a lower socioeconomic status, to investigate if it remains an accurate predictor of HFpEF.

Risks:

As the investigators study is a retrospective observational study there are no risks to participants, and all data obtained will be anonymised with no personally identifiable data being analysed.

Impact:

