The main outcome of this project will be whether the H2FPEF score is able to accurately predict HFpEF on the patient population of QAH, Portsmouth or if it overestimates diagnosis. If the investigator's research hypothesis is accepted then future research will be required to either optimise H2FPEF score or to develop new HFpEF diagnostic criteria. The enigma of HFpEF would continue to be the focus of research with the aim of developing an applicable clinical diagnostic tool. Alternatively if the investigators accept the null hypothesis then the H2FPEF score will have been validated on the population and would have the potential to be used by QAH and other trusts. Future research would then be required on other populations to further assess the generalisability of H2FPEF. The implications of this would be that patients are able to be diagnosed with HFpEF quicker and non-invasively requiring just an ECG, a focus echocardiogram and a routine clinical examination. Consequently invasive

cardiac catheterisation would not be required for diagnosis which would improve patient outcomes and patient service experience, as well as being cost-effective for the trust.

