7.2 Secondary Objectives

The investigator's secondary objectives are to:

- Investigate if H2FPEF overestimates HFpEF diagnosis on the patient population when compared against known BNP levels.
- To evaluate if H2FPEF can be validated on the patient population and be utilised to improve patient pathway for HFpEF.
- Follow patients up over one year to monitor outcomes

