8. STUDY DESIGN

8.1 Summary of Study Design

Data will be collected retrospectively from consecutive patients who meet the inclusion criteria to calculate a H2FPEF score: weight, number of hypertensive medications prescribed, presence of AF or not, presence of pulmonary hypertension or not, age and filling pressure. A total H2FPEF score will then be calculated for each patient as per Reddy et al. (2018) protocol: BMI > 30 kg/m² (2 points), ≥2 anti-hypertensive medications (1 point), paroxysmal or permanent AF (3 points), pulmonary artery systolic pressure >35mmHg (1 point), age >60 years (1 point), E/e' filling pressure > 9 (1 point).

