13.2 Analysis of Outcome Measures

To determine if the H2FPEF score was accurate in predicting HFpEF the calculated H2FPEF score will be compared against BNP blood test results using the cut-off points stated by the European Society of Cardiology (Ponikowski et al., 2016). To test our hypothesis an analysis of variance test (ANOVA) will be performed to provide one simultaneous evaluation of the data to determine if there is a significant difference between H2FPEF score and diagnosis of HFpEF. A logistic regression analysis will then be carried out to give an odds ratio and provide a predictive analysis of the data. All statistical analysis will be performed using SPSS software.

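### The ANOVA named as the hypothesis test measures discrimination, not overestimation; the measures that could show over-diagnosis have no stated threshold, and accepting the null is not validation

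*Combined protocol and SAP*

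**What the plan says.** The synopsis (section 2) states the hypothesis about H2FPEF in one direction: "that this will overestimate the probability of HFpEF". Section 5 gives the reason, that the component conditions are common and tend to occur together, "making it likely that it will over diagnose HFpEF". Section 7.2 makes it a secondary objective: "Investigate if H2FPEF overestimates HFpEF diagnosis on the patient population when compared against known BNP levels".

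Section 13.2 assigns the test: "To test our hypothesis an analysis of variance test (ANOVA) will be performed to provide one simultaneous evaluation of the data". The ANOVA is to look for a significant difference between score and diagnosis. A logistic regression giving an odds ratio follows. The synopsis lists the same ANOVA only as a secondary outcome measure ("ANOVA will be performed to provide one simultaneous evaluation of the data"). Its primary outcome measure is predictive accuracy by logistic regression, "with diagnostic accuracy being assessed by sensitivity and specificity calculations". Section 8.2 agrees on the primary measure, but section 13.2 mentions neither sensitivity nor specificity.

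Section 8.1 gives points for each item, for example "paroxysmal or permanent AF (3 points), pulmonary artery systolic pressure >35mmHg (1 point), age >60 years (1 point", but no total that counts as positive. The cut-offs mentioned in section 13.2 are natriuretic-peptide values, which define the reference diagnosis and not a positive score.

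Under Impact, section 5 states what follows from a null result: "Alternatively if the investigators accept the null hypothesis then the H2FPEF score will have been validated on the population". The null itself is not written out, and no alpha, margin or accuracy target is given.

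**The concern.** Overestimation means that the score labels more patients as HFpEF than have it, or gives them too high a probability. To see this, the score needs an anchor: a threshold that makes it positive, or a predicted probability to set against the observed proportion. A comparison of mean scores has neither. A significant ANOVA would show that the score separates the groups, which speaks for the score and not for the hypothesis. A non-significant one would suggest that it does not separate them, yet section 5 can be read as calling that validation.

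The stake is the study's stated use. Sections 2 and 5 link the result to use of the score in this Trust and others, or to a search for a different tool. If the threshold and the reference are settled after the data have been seen, the answer can fall on either side.

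**Working it through.** **The plan's own figure.** The synopsis gives a planned sample of 2000. No alpha, power, effect size, prevalence or precision target accompanies it, and section 10 takes all eligible patients from 2016, so there is no derivation to reproduce.

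**Inputs.** From section 8.1: item points 2, 1, 3, 1, 1, 1 (range 0 to 9). Assumed here: frequencies of those items, in that order, of 0.35, 0.40, 0.10, 0.20, 0.70, 0.40 without HFpEF and 0.50, 0.60, 0.35, 0.45, 0.88, 0.70 with it; items independent within each group; prevalence 0.5; n = 2000; alpha 0.05 two-sided. These give mean scores 2.70 and 4.68, variances 2.570 and 3.851, and AUC 0.778.

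**Step 1: what F measures.**
- Between-group sum of squares = (1000 × 1000 / 2000) × (4.68 - 2.70)² = 500 × 3.9204 = 1960.2.
- Within-group mean square = (1000 × 2.570 + 1000 × 3.851) / 1998 = 3.2135.
- F = 1960.2 / 3.2135 = 610.0.

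Adding a constant to every score changes neither the mean difference nor the variances, so F stays at 610.0. This holds for any data and needs none of the assumptions.

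**Step 2: what over-diagnosis measures.** Let D be the score-positive minus the reference-positive proportion. Then D = (1 - specificity)(1 - prevalence) - (1 - sensitivity)(prevalence). The 95% half-width is 1.96 × √[(discordant proportion - D²) / n].

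| Positive if score at least | Sensitivity | Specificity | False positive | False negative | D (95% CI) | F |
|---|---|---|---|---|---|---|
| 3 | 0.859 | 0.502 | 0.249 | 0.070 | +0.179 (0.155 to 0.202) | 610 |
| 4 | 0.694 | 0.711 | 0.144 | 0.153 | -0.009 (-0.032 to 0.015) | 610 |
| 5 | 0.519 | 0.868 | 0.066 | 0.241 | -0.175 (-0.198 to -0.152) | 610 |
| 6 | 0.328 | 0.949 | 0.026 | 0.336 | -0.310 (-0.333 to -0.288) | 610 |

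False positives and false negatives are proportions of all patients; D uses unrounded values.

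The same table shows the effect of a uniform shift. With the cut-off held at 4, one extra point for everybody is the same as cut-off 3 on the unshifted score, so D moves from -0.009 to +0.179. One point fewer gives -0.175. F is 610 in all three cases.

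**Step 3: prevalence.** With the same items, D from cut-off 3 to 6 runs from +0.306 to -0.166 at prevalence 0.3, and from -0.013 to -0.527 at prevalence 0.8. At 0.8 the value for cut-off 3 has a 95% CI of -0.033 to 0.007, which includes 0.

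**Step 4: what a significant ANOVA would mean.** With 1000 patients per group and 80% power, the detectable difference is (1.960 + 0.842) × √(1/1000 + 1/1000) = 0.125 SD. That is an AUC of Φ(0.125/√2) = 0.535, barely better than chance.

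**Step 5: the logistic regression.** A model refitted to these patients has a mean predicted probability equal to the observed prevalence, and adding a constant to every score leaves the odds ratio unchanged. In a separate simulated data set (scores binomial out of 9, probability 0.55 with and 0.40 without HFpEF, prevalence 0.5) the odds ratio was 1.879 before and after adding 2 points. The refitted model therefore cannot show overestimation either.

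**Step 6: accepting the null.** If the null is equal mean scores, a score unrelated to diagnosis keeps it about 95% of the time at alpha 0.05. If the null is that the score does not overestimate, a non-significant result still is not evidence of accuracy. Even a D near 0 is not: at cut-off 4, D is -0.009 while 0.144 + 0.153 = 0.297 of patients are misclassified.

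**The case against.** The strongest reply is that the ANOVA is only a secondary outcome measure in the synopsis, and that the primary measure, sensitivity and specificity, does bear on over-diagnosis. That stands in part. A reader might infer that the whole conclusion rests on the ANOVA; the documents do not say so. But section 13.2 is where the hypothesis is given its test, that test is the ANOVA, and the primary measures are absent there.

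A reader might also infer that the fault is a missing direction, to be cured by a one-sided test. It is not. The group means are visible, so the direction of their difference is known, but a higher mean in HFpEF still shows only discrimination.

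On the threshold, section 8.2 says that sensitivity and specificity come from logistic regression, which may mean classification at a predicted probability. That is a fair reading, but the probability threshold is not stated either. Section 8.1 also follows the original report's scoring, and that report may contain a cut-off. The claim here is only that this plan does not fix one.

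On the reference, section 13.2 (BNP), section 11.4 (ejection fraction and BNP) and section 5 (signs and symptoms, raised natriuretic peptide, ejection fraction of 50% or more) can be read as parts of one definition. They need stating together and are not necessarily in conflict.

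Finally, the item frequencies and prevalence above are invented, so the table illustrates the problem and forecasts nothing. Section 13.4 provides for consulting a statistician if queries arise, but that does not set a threshold or a criterion in advance.

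**Conclusion.** The point holds and should be settled before the data are analysed. The test named for the hypothesis measures the wrong quantity. The measures that could answer the question lack a threshold and are missing from the analysis section. The step from accepting the null to validation is unsound under any reading of the null.

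That F is blind to a uniform shift follows from algebra and needs no assumption. The size of the effect, D from +0.179 to -0.310 with F fixed at 610, rests on the assumed item frequencies, independence within groups, prevalence 0.5 and n = 2000. Other prevalences move the point at which the sign changes, and at 0.8 no cut-off from 3 to 6 gives a positive D.

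A reader should not infer that the study will in fact reach the wrong answer, or that H2FPEF does or does not overestimate HFpEF in this population. The documents support neither.

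**What to change.** 1. Remove the ANOVA as the hypothesis test, keep mean score by diagnosis as description only, and align the synopsis with section 13.2.
2. Before analysis, fix the score threshold or thresholds and one reference definition of HFpEF. State whether ejection fraction is part of it, reconciling sections 5, 11.4 and 13.2. Test over-diagnosis as the score-positive minus the reference-positive proportion with a paired 95% CI. Conclude that the score overestimates only if the interval lies wholly above 0, and say that this is relative to that reference and to this population's prevalence.
3. In section 13.2, report sensitivity and specificity at that threshold, and the AUC, each with a 95% CI.
4. Reword the synopsis hypothesis as over-diagnosis at the stated threshold instead of overestimated probability. Only if the team holds a published score-to-probability mapping, which these documents do not give, compare mean predicted with observed proportion, without refitting.
5. Delete the statement in section 5 that accepting the null validates the score. Base any validation statement on the CIs for sensitivity, specificity and the difference, judged against pre-stated limits.
6. Reconcile section 11.4, which records ejection fraction and BNP, with the form in section 12.1, which has no column for either, and with section 13.3, which limits collection to score data. The paired comparison cannot be run unless both are collected.

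The cost is wording, two or more form columns and a paired analysis of routine data; no new patients or tests. The team must agree a threshold, a reference and limits in advance. Precision depends on how many eligible patients are found: at prevalence 0.5 and cut-off 4 the half-width for D is 1.96 × √(0.297 / 2000) = 0.024, and twice that, 0.048, with 500.

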13.3 Procedure for Dealing with Missing, Unused and Spurious Data

Only data relating to the H2FPEF score will be collected; as per inclusion/ exclusion criteria no patient will be included in the study unless they had all of the necessary tests at their clinic visit. If no data is available for one year follow-up then the patient will be excluded from this assessment, but will still be included in the initial assessment of the H2FPEF diagnostic criterion.

13.4 Procedures for Reporting any Deviation(s) from the Original Statistical Analysis Plan

If any queries regarding statistical analysis are raised by any of the study team then a consultation with a qualified statistician will be undertaken to find a suitable solution that all members are satisfied with.

13.5 Interim analysis and criteria for early study termination

N/A

14. ETHICS

The main ethical issue associated with the investigator's study design is due to the retrospective nature of the data collection meaning that consent is unable to be obtained. However, all data is already stored on the heart failure clinic database at QAH from when they will have attended, with all tests being performed routinely as part of their clinical patient pathway. In addition no personally identifiable data will be used during analysis or results of the study. Patients will be anonymised during the initial data collection, with a separate document detailing pseudonymisation using patient hospital number only.

14.1 Participant Confidentiality

The study staff will ensure that the participants' anonymity is maintained. Only the relevant clinical data will be collected, and will only be accessed by members of the research team that are involved in the clinical care and would have access anyway. All documents will be stored securely on secured personal hospital drives with password protection and only accessible by study staff and authorised personnel. The study will comply with the Data Protection Act which requires data to be anonymised as soon as it is practical to do so.

14.2 Other Ethical Considerations

N/A

14.3 Declaration of Helsinki

Where appropriate the study protocol will be carried out in accordance with the Declaration of Helsinki: No unnecessary suffering will be caused to participants and the benefits of the study

outweigh any risks.

14.4 ICH Guidelines for Good Clinical Practice

All staff involved in the study will be GCP trained as per NIHR and will be monitored by the sponsor to ensure adherence to GCP.

15. PATIENT PUBLIC INVOLVEMENT (PPI)

15.1 Study design

This proposal originated from clinicians, with the proposal being presented to the PPI team at QAH for review. Review from PPI team was positive with agreement of the research background and requirement, as well as retrospective study design. Lay people will not be participating in data collection or analysis, but will be included as part of the ethical review panel and forming of lay summaries.

15.2 Study implementation

Public and patient involvement will be considered before data collection begins. Patient Research Ambassadors have been presented with and discussed to give their input and advice.

[figure not shown]
15.3 Dissemination

Initial study write-up will be submitted to Manchester Metropolitan University to satisfy the major project module of the primary investigators MSc programme. Results of the study will be presented at local and national conferences, as well as being submitted for journal publication. Patient Research Ambassadors will be invited for advice on areas for public dissemination of results.

16. FINANCING AND INSURANCE

This study is funded through The Scientist Training Programme (STP) as part of [name] Clinical Scientist training. Portsmouth Hospitals NHS Trust will be the sponsor of this study.

17. TIMETABLE AND ORGANISATIONAL CHART

18. RESOURCES, EQUIPMENT AND PHYSICAL FACILITIES

All of the study protocol will be carried out on a Portsmouth Hospitals NHS Trust computer at QAH

19. DISSEMINATION AND OUTCOME

Initial study write-up will be submitted to Manchester Metropolitan University to satisfy the major project module of the primary investigators MSc programme. Applications will be made to present study results at local level at Portsmouth Hospitals NHS Trust Healthcare Scientist conferences, as well as national conferences such as BSE. Final write-up of the study will also be submitted for journal publication.

